3.0 OBJECTIVES/STUDY AIMS

The goal of this study is to establish a research program – the Older Adult Hematologic Malignancy (OHM) program – that will address important gaps in data about how best to care for older adults with hematologic malignancies. It is clear that markers of frailty are important predictors of tolerance of therapy and survival, but few studies have assessed their value in this population. Geriatric assessment and co-management are associated with improvements in quality of life, resource utilization and survival, but have not been tested scientifically in hematologic malignancies. We therefore propose the following specific aims:

3.1 Specific Aim 1

Characterize the prognostic value of frailty as compared to clinical prognostic models for older patients with blood cancers. We will perform a combined frailty

assessment in patients 70 and older who present to DFCI with a new diagnosis of MDS or a hematologic malignancy. Patients will be categorized as robust, pre-frail or frail based on their frailty score. We will then determine how the presence or absence of frailty predicts important outcomes such as treatment, resource utilization and mortality. In a subset of patient who specifically agree, frailty will be re-assessed at subsequent visits.

Hypothesis: Frailty will predict survival for those older patients with low-risk disease on molecular markers/disease-based risk systems, but be trumped by these for patients with high-risk disease.

3.2 Specific Aim 2

Determine if co-management of frail and pre-frail older adults with blood cancers by an embedded geriatrician improves outcomes. Patients who score as pre-frail or frail will be randomized to geriatric assessment and co-management with a geriatrician or usual care. They will be followed for disease-specific outcomes, with the primary outcome being overall survival at 1 year.

[figure not shown]
Hypothesis: For those assessed to be frail with rigorous measurement, co-management by an embedded geriatrician will improve overall survival at one year.

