5.1 Patient Selection and Recruitment

All eligible patients will be given an in-person or virtual appointment with our clinical research coordinator before their first meeting with their hematologist to discuss the study; the type of appointment will depend on availability during the COVID-19 pandemic. This CRC will have been trained in frailty assessment by [name] and will be responsible for obtaining informed consent and completing the baseline frailty assessment for patients who consent. Importantly, patients will be able to consent to the baseline assessment, a potential follow-up assessment at a future visit, and/or allowing collection of extra samples for the laboratory. Categorical frailty status (robust versus frail/pre-frail) will be emailed to clinicians.

For Specific Aim 2 (now closed to enrollment), patients will be allowed to see a geriatrician outside of the trial design if they ask for this or if their physician requests it. We acknowledge that this may somewhat affect our randomized design, however, we feel that it is important to offer this service. Frail or pre-frail patients who were not randomized to geriatric co-management but who see a geriatrician anyway will first be analyzed in an intent-to-treat manner and then excluded from a secondary analysis to assess if this event affects overall findings.

As above, frail, pre-frail and robust patients will undergo additional prospective evaluation to assess for study outcomes: for Specific Aim 1 we will compare frail and pre-frail

patients who did not see a geriatrician to robust patients, and for Specific Aim 2, we will compare frail and pre-frail patients who saw a geriatrician to those who did not (see schema).

For all patients who go on to see a geriatrician, whether inside or outside of the trial design, continued follow-up (i.e. past the initial comprehensive geriatric assessment) will be determined by discussion between the geriatrician, the patient, and the patient's DFCI oncologist. As long as this resource remains available, patients will be able to follow-up with our geriatricians as long as they continue to receive their care at DFCI.

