5.4 Data Collection Procedures

Patients will be approached or contacted by the research assistant either at their scheduled appointment with the DFCI oncologist (in-person) or shortly after that appointment (virtual). The research assistant will then consent the patients and document consent with either the patient's wet-ink signature (in-person) or the signature of the research assistant verifying that verbal consent was given (virtual). The assessment will be conducted in-person or remotely, by phone or video conference, to preserve the safety of our patient population during the ongoing COVID-19 pandemic.

In-person assessments will begin with a 28-item self-report questionnaire (see appendix B) filled out by the patient. Next, the research assistant will administer the delayed recall section of the Montreal Cognitive Assessment (MoCA), clock-in-the-box test, grip strength test, and gait speed test. That will end the in-person frailty assessment. Virtual assessments contain minor changes to accommodate remote completion. The 28-item questionnaire, MoCA recall, and modified Clock Draw are conducted by the research assistant during a telehealth appointment. A patient caregiver will be trained to administer a remote gait speed test with a 4-meter strip of

ribbon that will be mailed in advance. Grip strength will be estimated using the following question: *“Do you have difficulty gripping with your hands (e.g. opening a jar)? Yes or No.”*

At baseline, the research assistant will perform a medical record review to obtain comorbidity information and body mass index. A follow up medical record review will be completed at one year from enrollment in order to obtain the outcome data listed in Table 3, which are all secondary outcomes of interest. There will also be general periodic assessments for overall survival.

Table 3: Summary of outcomes

Outcome:	Timeline for assessment:	Operationalization	Obtained from:
Survival*	6 months, 1 year	Overall survival	Patient medical record and outside records
Disease severity	Baseline	Disease Severity	Patient medical record and outside records
Treatment assignment	6 months	Supportive care only vs. chemotherapy vs. low dose chemotherapy vs. investigational treatment; any disease-modifying treatment versus not	Patient medical record and outside records
Hospitalizations	6 months	Number and length of hospitalizations since enrollment	Patient medical record and outside records

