Emergency department visits	6 months	Number of ED visits	Patient medical record and outside records
Code status documentation	6 months	Code status entered into the medical record	Patient medical record
Continuation of care at DFCI	6 months	Number of visits and length of follow-up at DFCI; receipt of treatment at DFCI	Patient medical record
Δ Number of medications	Baseline to 3 months	Overall number of medications = number of cancer meds + number of non cancer meds	Patient medical record
Δ Blood pressure	Baseline, 6 months	Measured at each visit	Patient medical record
Content Analysis of Notes	6 months	Only patients randomized to geriatrician	Patient medical record

*primary outcome

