6.0 ANALYTIC CONSIDERATIONS

6.1 Specific Aim 1

We will first perform descriptive analyses of covariates of frailty/pre-frailty in our population, including age, gender, race-ethnicity, and disease type. Means and proportions will be used to describe patient characteristics, individual and summary frailty responses, baseline clinical data, and treatment assignment. We will identify variables that are associated with the outcomes of interest using Kaplan-Meier curves and log-rank tests. Given limited numbers of patients and other study resources, we will plan to combine the frail and pre-frail groups in our analyses for Aim 1 (frail/pre-frail versus robust), but if power allows, we will also compare outcomes for all three groups (frail versus pre-frail versus robust). We will use the tests above for univariate analyses to determine whether any of the relevant geriatric domains, socio-demographic factors, or clinical data are associated with choice of treatment, length of time in the hospital and survival. We will also perform univariable and multivariable analyses to determine if frailty interacts with other patient characteristics to influence outcomes. We will also conduct analyses specific to disease clinics at DFCI (MDS/leukemia versus lymphoma versus myeloma). We will consider a p value < 0.05 to be significant, and all analyses will be carried out using SAS v.9.

6.2 Specific Aim 2

For frail patients, pre-frail patients and the combined cohort, we will create multivariable models to assess the impact of geriatric co-management on the outcomes listed in Table 3, controlling for age, gender, race-ethnicity, and disease type. We will consider a p value < 0.05 to be significant, and all analyses will be carried out using SAS v.9. Of note, we again plan to combine the frail and pre-frail groups in our analysis given limited resources and lack of current data as to whether or not geriatric intervention is more helpful in one of these groups; if power allows (see below), we will also adjust for frail versus pre-frail status.

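### The model for change in blood pressure omits baseline blood pressure, which costs precision on a secondary outcome, and the rule for choosing the 6-month reading is left open

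*Combined protocol and SAP*

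**What the plan says.** Table 3 in Section 5.4 defines the outcome as a change in blood pressure, in the row "Δ Blood pressure Baseline, 6 months Measured at each visit Patient medical record". The time points are "Baseline, 6 months", the whole operational rule is "Measured at each visit", and the source is the medical record. Section 5.4 adds that "A follow up medical record review will be completed at one year from enrollment", so values are extracted from routine care and the study schedules no blood pressure measurement of its own. The table does not state which visit or reading counts, what window applies around 6 months, or whether systolic or diastolic pressure is meant.

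Section 6.2 uses a single covariate set for all Table 3 outcomes, "controlling for age, gender, race-ethnicity, and disease type", with frail versus pre-frail status added if power allows. Baseline blood pressure is not mentioned. Under Section 6.4 randomisation is stratified by disease type only.

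Under Section 3.2 patients are "randomized to geriatric assessment and co-management with a geriatrician or usual care". Section 5.1 also says that "patients will be allowed to see a geriatrician outside of the trial design if they ask for this or if their physician requests it", and that for anyone who does see one, inside or outside the trial design, "patients will be able to follow-up with our geriatricians as long as they continue to receive their care at DFCI".

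**The concern.** A change score subtracts the whole baseline value, which is the right amount only if baseline and follow-up move one for one. When their correlation is below 1, patients who start high tend to fall and patients who start low tend to rise, whatever their arm. That regression to the mean stays in the residual of an unadjusted change model as noise. If the arms happen to start at different levels, part of the difference passes into the estimated effect. The stratification does not balance blood pressure, and none of the listed covariates is a substitute for the baseline reading.

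The second issue is how the 6-month value is picked. Without a rule, the person reviewing the record chooses among whatever readings exist, and an arm with more assigned visits may offer more of them. At stake is the precision and clarity of one secondary comparison. The primary outcome, overall survival at one year, is untouched.

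**Working it through.** The plan gives no effect size, standard deviation, correlation or power for blood pressure, so it has no figure to reproduce. Its only power statement (Section 6.3) concerns survival and has no bearing here.

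**Inputs.** From Section 6.3: 107 usual-care and 53 co-management patients. Assumed: correlation r between baseline and 6 months of 0.3 to 0.7; equal standard deviation s at both times, 15 or 20 mmHg; two-sided 5% test (Section 6.2 gives p < 0.05 without stating sidedness); a 5 mmHg true difference for illustration; a reading from every patient. The listed covariates appear in both models, so r is best read as the correlation remaining after them.

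**Step 1: variance.**
- Change score: 2(1 − r)s².
- Adjusted for baseline: (1 − r²)s².
- Ratio, adjusted to change: (1 − r²) / [2(1 − r)] = (1 + r)/2.

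| r | Ratio | Extra patients needed without adjustment, 2/(1 + r) − 1 |
|---|---|---|
| 0.3 | 0.65 | 54% |
| 0.5 | 0.75 | 33% |
| 0.7 | 0.85 | 18% |

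The ratio does not depend on s or on the split between arms. Nor does its direction depend on equal variances: with baseline and follow-up standard deviations a and b, the change-score variance exceeds the adjusted variance by (a − rb)², which is never negative.

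**Step 2: what this means with 107 and 53 patients.** The difference detectable with 80% power is (1.96 + 0.84) × SD × √(1/107 + 1/53), and the square root is 0.168. For s = 15 and r = 0.5 the change score has SD 15 × √1 = 15, and the adjusted analysis has SD 15 × √0.75 = 13.0.

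| s (mmHg) | r | Detectable difference, change → adjusted (mmHg) | Power for 5 mmHg, change → adjusted |
|---|---|---|---|
| 15 | 0.3 | 8.35 → 6.73 | 39% → 55% |
| 15 | 0.5 | 7.06 → 6.11 | 51% → 63% |
| 15 | 0.7 | 5.47 → 5.04 | 73% → 79% |
| 20 | 0.5 | 9.41 → 8.15 | 32% → 41% |
| 20 | 0.7 | 7.29 → 6.72 | 49% → 55% |

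**Step 3: chance imbalance.** Given a baseline difference d between arms, the unadjusted change comparison is off by (1 − r)d. For d = 5 mmHg this is 3.5, 2.5 and 1.5 mmHg at r = 0.3, 0.5 and 0.7. The standard error of the baseline difference is 0.168 × 15 = 2.5 mmHg, or 0.168 × 20 = 3.4 mmHg. So 5 mmHg is about 2 standard errors if s = 15 and about 1.5 if s = 20. A 2.5 mmHg imbalance gives 1.75, 1.25 and 0.75 mmHg.

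**Step 4: which reading is used.** Table 3 gives both arms the same time points and source but no selection rule. Section 3.2 assigns geriatric visits to one arm. Section 5.1 leaves the number of later visits to discussion and lets usual-care patients see a geriatrician on request. The pool of readings may therefore be unequal. The documents give nothing from which to size any resulting difference.

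**The case against.** The best defence is that the outcome is already a change, so baseline has been taken into account, and that randomisation makes the comparison fair. Half of this stands. The unadjusted comparison is unbiased on average, and a reader who infers bias from Step 3 goes too far: those figures are errors conditional on an imbalance that is possible but not typical. Subtracting baseline is nevertheless not the same as adjusting for it, and the variance loss in Step 1 remains.

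A reader might also infer that the two arms are measured differently. The documents do not support that. Time points and source are common to both arms, and oncology visits supply readings in both. Sections 1.0 and 3.2 describe the geriatrician as embedded in the oncology setting. Section 4.0 mentions separate geriatrician clinic days, but nothing says that staff or procedure differ, and no text ties the 6-month value to a geriatrician visit. Nor are those visits strictly confined to one arm, given the off-trial access in Section 5.1.

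Oncology visits were also frequent. Section 2.1 gives 3429/674 = 5.1, 1704/318 = 5.4 and 3245/516 = 6.3 visits per patient in a year. If they were evenly spaced (an assumption), the longest interval is 12/5.1 = 2.4 months, so some reading would lie within about 1.2 months of the 6-month point. What remains is an undefined rule that permits a difference between arms.

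Finally, this is one of several secondary outcomes, with no hypothesis or power claim attached. That limits the importance of the point but does not remove it.

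**Conclusion.** The point holds as a free improvement. Leaving baseline blood pressure out of the Section 6.2 model gives up precision that the collected data could supply. Adjusting would reduce residual variance by 15-35% for r between 0.7 and 0.3, and would remove the error from chance imbalance to the extent that the relation to baseline is linear. The percentages rest on the assumed r and on equal variances; that adjustment does not increase the residual variance rests on neither. The mmHg and power figures also rest on assumed standard deviations and on a reading from every patient, so deaths or missing readings before 6 months would make both analyses weaker.

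The open rule for the 6-month reading is a lesser matter of definition. It creates a possibility of unequal ascertainment, not a demonstrated one. Neither issue affects the primary survival comparison.

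**What to change.** 1. **Section 6.2:** for change in blood pressure, add the baseline reading as a covariate alongside those listed. The treatment estimate is then the same whether the dependent variable is the change or the 6-month value.
2. **Table 3:** state one rule for both arms, for example the oncology-visit reading closest to 6 months within a named window, with baseline from the enrolment oncology visit. Say whether systolic or diastolic pressure is analysed, and how missing readings and deaths before 6 months are handled.

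The first change costs one degree of freedom and loses no patients, because anyone without a baseline reading already has no change value. The second has a small cost: readings from geriatrician visits are not used in the comparison. Neither needs new visits or alters care.

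Section 5.1 records that Aim 2 has closed to enrolment, and Section 8.0 scheduled its final manuscript to end in January 2020. Both changes therefore apply to analysis and reporting. If they are made after the data were seen, they should be labelled as such, with the analysis as listed in Section 6.2 reported beside them.

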5.5 Laboratory Correlates

We have engaged [name], [name], [name] and [name] as active members of the OHM team. We are hopeful that our new infrastructure for the rapid identification and provision of samples to their labs (one of the CRC duties, see below) will result in acceleration of current efforts at characterizing hematopoietic events specific to the elderly with blood cancers. Each week, we will provide them with de-identified list of patients -- gender, age and malignancy type -- who have consented to extra samples and are coming in for blood draw and/or marrow. These samples will serve as a source of controls for ongoing studies focusing on how age-related changes in hematopoietic progenitor subsets, changes in the bone marrow, and in circulating levels of cytokines observed in healthy older individuals may evolve into frank cancer. They will also serve as a source of overt cancer samples to compare to candidate markers from the new pre-cursor clinic, which is expected to contain many elderly patients.

More specifically, we have identified a potential biomarker of interest, p16^{INK4a}, a tumor suppressor protein in the peripheral blood as an objective measure to elucidate the association between frailty and disease genetics.²⁸ Patients who have consented to providing additional samples from blood tests and return to Dana-Farber will have their p16^{INK4a} levels measured. The samples will be collected from DFCI Lab Services and then processed by personnel in the [name] lab. All forms of patient identification associated with the sample will be removed and coded only with the corresponding OHM patient identification number. If the patient's frailty assessment is more than two weeks old, we will also approach the patient to conduct a second assessment.

We will measure p16^{INK4a} expression from peripheral blood T-cells isolated by magnetic bead separation, where CD3+ and CD3- fractions will be isolated, cell pellets flash frozen, and additional aliquots viably cryopreserved in 10% DMSO. Total RNA will be isolated from CD3+ T cell pellets and p16^{INK4a} expression will be measured using a validated Nanostring assay developed by the [name] lab at Ohio State University. As the characterization of p16^{INK4a} is only available at OSU, we will be procuring the services of [name] lab as an external resource to analyze p16^{INK4a} levels in our samples. To facilitate preliminary analyses and to be able to combine with existing p16^{INK4a} normative data at OSU, [name] lab will be sent limited clinical data for each sample: age, gender, malignancy, frailty status, and ECOG score. Of note, these data will only be linked to participants via study ID; [name] lab will not be sent participants' names, medical record numbers, dates of birth, or any other identifying data. Both the study data and the resulting analyses will be sent electronically as secure and encrypted files.

Additionally, stored cell pellets and cryopreserved cells will be used for orthogonal validation experiments in the [name] lab, including additional sorting of viable cells (e.g., if other cell types, or subpopulations within CD3+ T cells are suggested to be relevant based on our pilot studies or others' data). Individual patient samples in the [name] lab will be destroyed one year after enrollment of the last participant of the study.

The integration of molecular diagnostics could lead to a new paradigm at the population level. These data may allow some (robust) older patients with blood cancers appropriately receive full-dose treatment despite their advanced age, and others (frail) are protected from unnecessary morbidity arising from the same. It also addresses issues relevant to the unequal burden of cancer and outcomes in diverse populations, as the frail elderly have both a higher incidence of cancer and also experience generally less favorable outcomes.

6.0 ANALYTIC CONSIDERATIONS

6.1 Specific Aim 1

We will first perform descriptive analyses of covariates of frailty/pre-frailty in our population, including age, gender, race-ethnicity, and disease type. Means and proportions will be used to describe patient characteristics, individual and summary frailty responses, baseline clinical data, and treatment assignment. We will identify variables that are associated with the outcomes of interest using Kaplan-Meier curves and log-rank tests. Given limited numbers of patients and other study resources, we will plan to combine the frail and pre-frail groups in our analyses for Aim 1 (frail/pre-frail versus robust), but if power allows, we will also compare outcomes for all three groups (frail versus pre-frail versus robust). We will use the tests above for univariate analyses to determine whether any of the relevant geriatric domains, socio-demographic factors, or clinical data are associated with choice of treatment, length of time in the hospital and survival. We will also perform univariable and multivariable analyses to determine if frailty interacts with other patient characteristics to influence outcomes. We will also conduct analyses specific to disease clinics at DFCI (MDS/leukemia versus lymphoma versus myeloma). We will consider a p value < 0.05 to be significant, and all analyses will be carried out using SAS v.9.

6.2 Specific Aim 2

For frail patients, pre-frail patients and the combined cohort, we will create multivariable models to assess the impact of geriatric co-management on the outcomes listed in Table 3, controlling for age, gender, race-ethnicity, and disease type. We will consider a p value < 0.05 to be significant, and all analyses will be carried out using SAS v.9. Of note, we again plan to combine the frail and pre-frail groups in our analysis given limited resources and lack of current data as to whether or not geriatric intervention is more helpful in one of these groups; if power allows (see below), we will also adjust for frail versus pre-frail status.

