There are many frailty models, but two of the most commonly used models are the phenotype model and the cumulative deficit model.¹⁰ The phenotype model is a categorical model that uses 5 separate variables to identify frailty. The variables are interrelated and are indicative of decreased physiologic reserve and resistance to stressors, two conditions that constitute the clinical definition of frailty.³ The phenotype model is also popular because of its clinical reproducibility.¹¹ The cumulative deficit model is a continuous model of frailty that uses assessment of a large index of symptoms to determine frailty status,^{10,12} with a higher number of symptoms leading to a greater likelihood of being frail.^{10,13} The cumulative deficit model is popular because it can evaluate impairments in many biological systems, is graded, and is conceptually simple.¹³

Rockwood and Mitnitski created a standard cumulative deficit approach with their Comprehensive Geriatric Assessment (CGA), with approximately 40 variables, some of which are self-reported (e.g. “how would you rate your health?”), others are ascertained by tests such as the Montreal Cognitive Assessment (MoCA)¹⁴, and others are determined by clinical evaluation (e.g. high blood pressure).¹⁵ The efficacy of this model was examined by Searle et al. in a 2008 study, which analyzed a group of 754 community dwelling elderly people who were assessed and then longitudinally followed for outcomes.¹² The study found that the CGA was a significant predictor of mortality.

Sheppard et al. examined a cohort of 1,288 older women with breast cancer in order to validate use of this frailty index in a cancer population, aiming to assess its utility in predicting non-initiation or discontinuation of adjuvant hormonal therapy.¹⁶ The investigators used a 35-item index adapted from the Searle approach. The index included self-reported items relating to limitations in basic and instrumental activities of daily living, sensory deficits, functioning, and the pre-diagnosis of comorbidity. They did not include measures of cognitive impairment, because women with cognitive impairment were excluded.

After calculating frailty scores on the 0-1 scale, cut-points of 0-0.2 for “robust”, 0.2-0.35 for “pre-frail”, and 0.35-1.0 for “Frail” were used. The study found that both frailty and pre-

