6.3 Power Considerations

Power analysis is based on Specific Aim 2, as the patients enrolled therein will be a subset of the patients from Specific Aim 1. The study is powered to detect a difference in the one-year overall survival rate (i.e., the primary endpoint) between the two groups in Specific Aim 2: those patients who see a geriatrician (Group 2) and those who do not (Group 1). Based on prior observational data, overall survival in Group 1 is expected to be 68% at one year (this is based on the one-year OS of a sample of 114 MDS patients followed at DFCI from 2006 to 2012). We expect the one-year overall survival rate in Group 2 (the intervention group) to be 85%, which corresponds a 25% of improvement over Group 1. A total sample size of 160 (107 Group 1; 53 Group 2) would achieve 80% power to detect this difference, at 0.05 one-sided type I error level.

Indeed, the number of patients seen in the OHM program will be limited by the resources of the CRC and the geriatricians. In one year, given current numbers, we would expect 600 unique myeloma, lymphoma and AML/MDS patients over aged 75 (see above) to present at DFCI. We will be aiming to undertake baseline assessments for all new patients appearing on four calendar days each week. We originally hoped to have 540 potential patients for Specific Aim 1. As of December 18, 2017, 494 patients out of the 570 patients approached (87%) have agreed to Specific Aim 1. Given our line of success with enrolling patients since February 3, 2015, and after discussions with our clinicians, we hope to recruit three times the number of

patients originally planned for this aim in order to conduct disease-specific analyses. We hope to have 1,620 potential patients for Specific Aim 1 so we may stratify analyses by our three disease-specific clinics at DFCI (MDS/leukemia, lymphoma, and myeloma).

If 216 (60%) of the 540 patients, originally planned for accrual, are ultimately assessed by the CRC, and 25% found to be frail or pre-frail continue to receive care at DFCI, and agree to the RCT, this leaves 54 to be randomized to geriatric co-management vs. routine oncology care (27 in each group) per year. Our hope is to reach a sample size of 160 patients (107 Group 1; 53 Group 2) for Specific Aim 2 in three years, but we will extend the study until we achieve this enrollment. Of note, we have expanded our geriatrician clinics to two sessions per week to accommodate this increased patient load.

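### Aim 1's main contrast merges frail with pre-frail and leaves the continuous frailty index unused; limited numbers do not justify that over a continuous score or an ordered trend

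*Combined protocol and SAP*

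**What the plan says.** Section 6.1 of the combined protocol and SAP states that "we will plan to combine the frail and pre-frail groups in our analyses for Aim 1 (frail/pre-frail versus robust"). The reason given is "Given limited numbers of patients and other study resources". The same sentence adds that "if power allows, we will also compare outcomes for all three groups (frail versus pre-frail versus robust"), without saying how much power is enough or who decides.

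Section 2.2 says that "The cumulative deficit model is a continuous model of frailty". Section 5.3 computes it from 43 items on a 0-1 scale and then cuts it at 0.2 and 0.35. Section 5.3 also computes the phenotype, a count of 0 to 5 factors cut into none, 1-2 and 3 or more. Section 6.1 does not say which of the two scores defines the Aim 1 groups. It describes frailty responses by means and proportions and tests separate geriatric domains one at a time, but no stated outcome model uses the total index as a continuous variable.

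On size, section 6.3 says "We originally hoped to have 540 potential patients for Specific Aim 1" and now "We hope to have 1,620 potential patients for Specific Aim 1 so we may stratify analyses by our three disease-specific clinics at DFCI". The power calculation in that section is for Aim 2 only.

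**The concern.** Aim 1 asks how much frailty contributes to prognosis beside disease-based measures. Its hypothesis in section 3.1 is an interaction: frailty should predict survival in low-risk disease and be overridden in high-risk disease. Section 6.1 also plans separate analyses by disease clinic. Interaction and subgroup analyses are where information is scarcest.

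The merged group puts a patient with one phenotype factor beside one with five, and an index of 0.21 beside one above 0.35. Section 2.2 reports, for the phenotype, that pre-frail people had outcomes between those of the robust and the frail, so the documents' own evidence points to graded risk. Under graded risk a two-group variable measures frailty's contribution with less power. A null result in high-risk disease could then reflect lost information and yet be read as support for the hypothesis.

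**Working it through.** **1. The plan's own figure.** The Aim 1 target is three times the original: 3 × 540 = 1,620, which reproduces exactly. Split equally over three clinics it is 1,620 / 3 = 540 per clinic. There is no Aim 1 power figure to reproduce.

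**2. Information kept by a binary cut (assumed: roughly normal index, log-linear risk).** With a proportion p on one side, the share kept is φ(z_p)² / [p(1 − p)].
- p = 0.20: 0.2800² / 0.16 = 0.490
- p = 0.25: 0.3178² / 0.1875 = 0.539
- p = 0.50: 0.3989² / 0.25 = 0.637

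**3. Information kept by scoring robust/pre-frail/frail as 0/1/2 (same assumptions).** With cut-offs a and b on the standard normal scale, the share is [φ(a) + φ(b)]² / Var(score).
- 20% robust, 5% frail: (0.2800 + 0.1031)² / 0.2275 = 0.645
- 25% robust, 25% frail: (0.3178 + 0.3178)² / 0.5 = 0.808

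Over 20-50% robust and 5-40% frail the range is about 65-81%. It depends on the frail proportion, which the documents do not give.

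**4. A worked example with the plan's cut-points.** Assumed, not in the documents: beta-distributed index with mean 0.22 and SD 0.12, HR 1.2 per SD, two-sided 0.05. Two death rates are used. The 32% is 1 − 0.68 from section 6.3, which comes from an MDS sample and was used for Aim 2. The 15% is an assumption, equal to 1 − 0.85 from the Aim 2 intervention group.

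The cut at 0.2 puts 50.8% in the merged group. Mean index is 0.123 below the cut and 0.314 above it. Share kept = 0.492 × 0.508 × (0.3136 − 0.1233)² / 0.12² = 0.629. The 0/1/2 score keeps 0.827.

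Power comes from a noncentral chi-square with noncentrality = deaths × (ln 1.2)² × share kept, where (ln 1.2)² = 0.03324. For 1,620 patients and 15% deaths there are 243 deaths: 243 × 0.03324 = 8.08 for the continuous index, and 8.08 × 0.629 = 5.08 for two groups.

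| N | Deaths | Continuous, 1 df | Two groups, 1 df | 0/1/2 trend, 1 df | Three unordered groups, 2 df |
|---|---|---|---|---|---|
| 1,620 | 15% (243) | 81% | 62% | 73% | 63% |
| 1,620 | 32% (518) | 99% | 91% | 97% | 93% |
| 540 | 15% (81) | 37% | 26% | 32% | 25% |
| 540 | 32% (173) | 67% | 48% | 59% | 48% |

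**5. Two groups against three unordered groups.** In the table these are close. The order depends on prevalence. With 1,620 patients, 15% deaths and HR 1.2, a beta index with mean 0.15 and SD 0.10 (27% frail/pre-frail) gives 63.6% for two groups and 59.0% for three. Mean 0.28 and SD 0.13 (70%) gives 53.5% and 63.0%.

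**The case against.** The strongest reply is that section 6.1 is choosing between two and three groups, and that few patients are a fair reason not to spend a second degree of freedom. This stands in part: step 5 shows that merging can cost nothing, or gain a little, against an unordered three-group test. A reader might infer that the stated reason is simply backwards. The documents do not support that. It fails only against a continuous score or a one-degree-of-freedom trend, options that the section does not consider. The conditional three-group comparison also means that the plan does not ignore the gradient altogether.

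A reader might also infer that tripling the target has removed the shortage. It has not: the 1,620 are potential patients, sought for three clinic-specific analyses, and an equal split returns each clinic to the original 540. Section 5.1 further limits the frail/pre-frail side of Aim 1 to those who did not see a geriatrician, so fewer than 1,620 may be analysed. For these reasons the loss should not be expressed as a number of patients thrown away.

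Third, the loss assumes graded risk. If risk were a pure step at 0.2, the two-group variable would be the more powerful. That stands as a caution, and is why a non-linearity check and the retained contrast are needed.

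Last, two groups match the robust versus frail/pre-frail result sent to clinicians (section 5.1). That is a good reason to report the contrast, but not to make it the only firm analysis.

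**Conclusion.** The point holds as a worthwhile improvement, not as a flaw that invalidates Aim 1. The main exposure is coarser than the data collected, and limited numbers do not explain why an analysis using the full score at the same cost in degrees of freedom was left out. Under graded risk, the two-group cut keeps roughly half to two-thirds of the information. The consequence could be small for the pooled analysis if deaths are frequent (99% to 91%), and larger within one clinic (67% to 48%, or about 37% to 26% with fewer deaths).

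All of these sizes rest on an assumed index distribution, event rate, effect and graded risk. They model the cumulative-deficit index alone, while section 6.1 leaves open which score defines the groups. A reader might go further and infer that the merged variable tilts the comparison towards the clinical prognostic models. The documents do not establish this: they specify neither the form of those models nor a metric for the comparison.

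**What to change.** In section 6.1:
- Name the cumulative-deficit index, per 0.1 and with a spline check for non-linearity, as the main exposure in the Aim 1 survival, interaction and clinic-specific models.
- Analyse the phenotype in parallel, as its ordered 0-5 count or as a one-degree-of-freedom trend over robust, pre-frail and frail, since the study means to validate both models.
- Replace the conditional three-group test with that trend, which removes the undefined power condition.
- Keep frail/pre-frail versus robust for Kaplan-Meier display and as a secondary contrast, and state which score defines it.
- State how the section 5.1 restriction on patients who saw a geriatrician applies in the continuous models.

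No new data are needed. The cost is one or two extra models per outcome, and an effect per 0.1 that is slightly less intuitive than a two-group comparison. Section 8.0 lists interim Aim 1 analyses, so the change should be dated and recorded as made without regard to their results.
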